14.3.8 Analysis of secondary endpoints

The analysis of the below dichotomous secondary endpoints will be based on the primary analyses of the primary estimand as specified above for the primary dichotomous endpoint.

For the continuous secondary endpoints, the analysis will be based on the primary (MMRM) analyses of the secondary estimand as specified above for the key secondary continuous endpoint.

The dichotomous secondary endpoints EASI90 at Week 16 and EASI50 at Week 16 will be analysed according to the primary analysis of the primary estimand as specified above for the primary endpoints.

The percentage change from baseline to Week 16 in EASI score and the change from baseline to Week 16 in Worst Daily Pruritus NRS weekly average, Eczema-related Sleep NRS (weekly average), and POEM will be analysed according to the primary (MMRM) analysis of the secondary estimand for the continuous key secondary endpoints.

14.3.9 Analysis of other endpoints

The binary other endpoints, reduction from baseline to Week 16 of DLQI ≥ 4 points among subjects with baseline DLQI ≥ 4 and reduction from baseline to Week 16 of POEM score ≥ 4 points in subjects with baseline POEM score ≥ 4 , will be summarised by treatment group.

To evaluate the efficacy related to health care resource utilisation, the amount of TCS used (assessed as the amount of TCS used between visits), and the cumulative amount of TCS used will be determined by 2-week periods. The amount of TCS used and the cumulative amount of TCS used will each be logarithm-transformed prior to analysis. Due to potential zero valued ‘amount of TCS used’, 1 will be added to the values prior to transformation. This transformation has in a similar trial proven the model below to fit data better compared to leaving the data untransformed. Data will be analysed by a repeated measurements model with an unstructured covariance matrix and the mean modelled as follows:

$$\text{Log}(Y+1) = \text{treatment} \times \text{visit} + \text{baseline IGA}$$

where ‘Y’ is either the amount of TCS used or the cumulative amount of TCS used. Data obtained after permanent discontinuation of IMP or after initiation of rescue treatment will be excluded from the analyses.

The estimated parameters will be transformed back to the original scale using the exponential function, thus producing estimated geometric means and estimated ratio of means which will be presented together with 95% CIs.

Results obtained after initiation of rescue treatment will be excluded from the analyses.

In addition, TCS use (AxMP) <5 g at Week 16 will be analysed according to the primary analysis of the primary estimand for the primary endpoint.

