9.2.2 Administration of AxMP (TCS)

The IRT will assign the required AxMP (TCS) kit number for each subject at each AxMP dispensing visit. The AxMP dispensing visits are shown in the schedule of trial procedures (Section [4](#)). The subject must return used and unused AxMP (TCS tubes) at each subsequent trial visit to assess the amount of TCS used. The subjects must be instructed by the site staff on the importance of returning all used and unused TCS tubes. The site staff will return used and unused TCS tubes to the contract manufacturing organisation (CMO). The returned TCS tubes will be weighed at the CMO.

Each subject will be instructed to apply a thin film of the dispensed AxMP (TCS) once daily on active lesions of AD, as needed. The TCS should be discontinued when control is achieved; discontinuation should preferably be gradual, and the maximum duration of a treatment course should not exceed 3 weeks. The safety and appropriateness of continued or repeated courses of TCS therapy will be monitored and supervised by site staff.

The AxMP (TCS) should be the only TCS product applied to the body during this period. Lower potency TCS or TCI may be used at the investigator's discretion on areas of the body where use of the supplied AxMP (TCS) is not advisable such as areas of thin skin (face, skin fold areas, genital areas, etc.) or on areas where continued treatment is considered unsafe. The low potency TCS and TCI will not be provided by LEO Pharma and will not be weighed but must be registered in the eCRF as concomitant medications (Section 9.6).

The supplied AxMP (TCS) is only for use on active lesions of AD and not for use in other indications.

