11.2.5 Body surface area involvement

The total BSA affected by AD will be assessed by the investigator for each section of the body as component A of SCORAD (Section 11.3.3) and will be reported as a percentage of all major body sections combined. The following body regions will be assessed (brackets show the highest possible score for each region): head and neck (9%), anterior trunk (18%), back (18%), upper limbs (18%), lower limbs (36%), and genitals (1%). The total BSA score will be assessed according to the schedule of procedures in Section 4.

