14.3.7.2 Secondary estimand for the continuous key secondary endpoints: 'hypothetical'

The secondary estimand for the continuous secondary endpoints will be:

- Treatment difference in change from baseline to Week 16 in SCORAD and DLQI, respectively, if all subjects adhered to the treatment regimen in the sense that they did not discontinue IMP permanently and no rescue medication was made available before Week 16.

The secondary estimand assesses the expected benefit when adhering to the treatment regimen tralokinumab+TCS with no rescue medication as compared to a treatment regimen with placebo+TCS with no rescue medication.

Primary analysis for the secondary estimand - continuous key secondary endpoints

Data collected after permanent discontinuation of IMP or after initiation of rescue medication will not be included in the analysis. For subjects without any post-baseline data, the baseline value will be carried forward as the first post-baseline assessment, corresponding to imputing a change of 0 at the first post-baseline assessment. This is to ensure that all subjects will be included in the analysis. The endpoints will be analysed using a repeated measurements model on the post-baseline responses up to Week 16 with an unstructured covariance matrix, Kenward-Roger approximation to estimate denominator degrees of freedom, and the mean modelled as follows (shown for change from baseline in SCORAD):

Change from baseline in SCORAD

= treatment \times visit + baseline SCORAD \times visit + baseline IGA

This model assumes that data is missing at random within each treatment arm. The estimates will be presented with 95% CI at each visit. The primary comparison between tralokinumab+TCS and placebo+TCS will be at Week 16.

Sensitivity analysis for secondary estimand - continuous key secondary endpoints

Rather than assuming that observations are missing at random within each treatment arm it is assumed that missing data from subjects who discontinue IMP/receive rescue medication in the tralokinumab+TCS arm will resemble data from subjects from the placebo+TCS arm who do not discontinue IMP/receive rescue medication.

Imputation of missing data at Week 16 will be done using a pattern mixture model where missing data in the tralokinumab+TCS arm as well as the placebo+TCS arm will be imputed from the placebo+TCS arm (using multiple imputations in a so-called copy-reference approach).

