Appendix 7: Short version of eligibility criteria

A short form (maximum 200 characters) version of each eligibility criteria for the trial is provided below.

No.	Inclusion criteria
1	Signed and dated informed consent has been obtained prior to any protocol-related procedures
2	Japanese subject aged 18 years and above
3	Diagnosis of AD as defined by the Hanifin and Rajka (1980) criteria for AD
4	History of AD for 1 year or more
5	Subjects with a recent history within 1 year before screening of inadequate response to treatment with topical medication or subjects for whom topical treatments are otherwise medically inadvisable
6	AD involvement of 10% (or more) body surface area at screening and at baseline according to component A of SCORAD
7	EASI score of 12 or more at screening and 16 or more at baseline
8	IGA score of 3 or more at screening and at baseline
9	Worst Daily Pruritus NRS average score of 4 or more during the week prior to baseline
10	Subjects must have applied a stable dose of emollient twice daily (or more, as needed) for at least 14 days before randomisation
11	Women of child bearing potential must use a highly effective form of birth control, confirmed by the investigator, throughout the trial and at least for 16 weeks after last administration of IMP

Abbreviation: AD, atopic dermatitis; EASI, Eczema Area and Severity Score; IGA, Investigator's Global Assessment; IMP, investigational medicinal product; NRS, numeric rating scale; SCORAD, Scoring Atopic Dermatitis.

No.	Exclusion criteria
1	Subjects for whom TCS are medically inadvisable in the opinion of the investigator
2	Concurrent enrolment in another interventional clinical trial
3	Previous randomisation in a tralokinumab clinical trial
4	Active dermatologic conditions that may confound the diagnosis of AD or would interfere with assessment of treatment, such as scabies, cutaneous lymphoma, or psoriasis
5	Known active allergic or irritant contact dermatitis that is likely to interfere with the assessment of severity of AD
6	Use of tanning beds or phototherapy (NBUVB, UVB, UVA1, PUVA) within 6 weeks prior to randomisation
7	Treatment with systemic immunosuppressive/immunomodulating drugs, systemic corticosteroids, or bleach baths within 4 weeks prior to randomisation
8	Treatment with TCS, TCI, topical PDE-4 inhibitors, or topical JAK inhibitors within 2 weeks prior to randomisation

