The amount of TCS used will be calculated as specified in section 6.6.6 and analysed in two ways, reflecting the two consumption assumptions. The primary analysis will be using the most conservative assumption that all missing tubes were fully used. The second assumption will be used as a sensitivity analysis, reflecting the primary analysis's extreme opposite, that all non-returned tubes were not used. The method used for analysis will be the one specified in the protocol. Additionally, descriptive histograms of both consumption assumptions will be produced.

Number of days without topical treatment use

The number of days without topical treatment use (collected as Patient Days of Topical Treatment Use in the eDiary) will be determined over 1-week periods from Week 0 until Week 16 and will be summarised over time by treatment group as specified in the protocol. Number of days without topical treatment use will be calculated using the same rules as for the Worst Daily Pruritus NRS (weekly average). In addition, a new binary endpoint '5-7 days without topical treatment use' will be introduced. This new endpoint will be evaluated by week and by treatment group as described for the primary analysis of the primary estimand ('composite') for the primary efficacy endpoints.

Scoring of PROs

POEM	Scored according to: https://www.nottingham.ac.uk/research/groups/cebd/documents/methodological-resources/poem-for-self-completion.pdf
DLQI	Scored according to: http://sites.cardiff.ac.uk/dermatology/quality-of-life/dermatology-quality-of-life-index-dlqi/dlqi-instructions-for-use-and-scoring/

Trial ID: LP0162-1343	Date: 15-Jun-2021	Version: 1.0 Page 13 of 22
-----------------------	-------------------	-------------------------------

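### The TCS-amount model is valid but omits baseline lesion extent, so its intervals may be somewhat wider than the collected data require

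*Protocol*

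**What the plan says.** Protocol 14.3.9 analyses the TCS used per two-week period and the cumulative TCS used, each as log(Y+1): "Data will be analysed by a repeated measurements model with an unstructured covariance matrix and the mean modelled as follows". The stated mean is treatment by visit plus baseline IGA. Results are back-transformed to geometric means and their ratio, with 95% intervals. SAP 6.6.4, under the amount of TCS used, adds two assumptions about unreturned tubes but leaves the model alone: "The method used for analysis will be the one specified in the protocol".

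Protocol 9.2.2 links use of the cream to lesions. Subjects are told to "apply a thin film of the dispensed AxMP (TCS) once daily on active lesions of AD, as needed".

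Extent is recorded at baseline. Protocol 11.2.5 says "The total BSA affected by AD will be assessed by the investigator for each section of the body as component A of SCORAD", and Panel 2 schedules this at screening and baseline. The eligibility list in Appendix 7 requires "AD involvement of 10% (or more) body surface area at screening and at baseline according to component A of SCORAD". Neither document puts BSA or another extent measure into the TCS model, or explains its absence.

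**The concern.** The amount of cream used should depend partly on how much skin is affected. The only baseline term in the model is a two-level severity grade, which Panel 6 describes mainly by erythema and papulation or infiltration. BSA may range from 10% to 100% among eligible subjects. Any part of that variation that predicts cream use beyond IGA stays in the residual.

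What is at stake is the width of the intervals. Protocol 14.3.5 plans no formal testing, so the estimate and its interval are the whole result, and there are only about 50 subjects per arm. The TCS endpoints are also the means by which Protocol 14.3.9 evaluates health care resource utilisation, a named part of the secondary efficacy objective.

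**Working it through.** **No stated figure to reproduce.** The documents give no SD, correlation, interval width or power for TCS amount. Protocol 14.1 sets the sample size without a precision calculation.

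**Inputs**
- N = 100, allocated 1:1, stratified by IGA 3 or 4 (Protocol 14.1).
- Two-sided 95% intervals (Protocol 14.3.5).
- Current model at one visit: 3 mean parameters (intercept, treatment, IGA). With one extent covariate: 4.
- r, the partial correlation of log(Y+1) with baseline extent given arm and IGA. This is assumed, from 0 to 0.5.

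**Formula.** Expected log-scale interval width with the extent term, divided by width without it, at one visit with complete data:

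ratio = √(1 − r²) × √[(N − 4)/(N − 5)] × t(0.975, N − 4)/t(0.975, N − 3)

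The first factor is the gain from removing explained variance. The other two are the cost of estimating one more slope. At N = 100 they multiply to 1.0054.

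Example at r = 0.3: √0.91 × 1.0054 = 0.9539 × 1.0054 = 0.959.

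The simulated column is a check: 3,000 trials per value of r, N = 100, 1:1 within IGA stratum, least squares with and without the covariate. Equivalent N is 100 / [(1 − r²) × 96/95].

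| r (assumed) | Ratio, formula | Ratio, simulated | Change in width | Equivalent N |
|---|---|---|---|---|
| 0 | 1.0054 | 1.0053 | 0.5% wider | 99.0 |
| 0.1 | 1.0003 | 1.0005 | none | 100.0 |
| 0.2 | 0.9851 | 0.9860 | 1.5% narrower | 103.1 |
| 0.3 | 0.9591 | 0.9596 | 4.1% narrower | 108.7 |
| 0.4 | 0.9214 | 0.9226 | 7.9% narrower | 117.8 |
| 0.5 | 0.8707 | 0.8723 | 12.9% narrower | 131.9 |

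**Break-even.** Setting the ratio to 1 gives √(1 − r²) = 1/1.0054, so r² ≈ 0.0107 and r ≈ 0.10.

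**Fewer subjects.** With N = 90 the ratios at r = 0.2, 0.3, 0.4 and 0.5 are 0.9857, 0.9597, 0.9220 and 0.8712, almost the same.

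**On the reported scale.** Assume a residual log-scale SD of 1.0, which the documents do not give, and 50 per arm. The standard error is 1.0 × √(2/50) = 0.20, so the interval for the ratio of geometric means is the estimate multiplied or divided by exp(1.96 × 0.20) = 1.48. Multiplying the standard error by √(1 − r²), and ignoring the small cost of the extra slope, gives 1.47 at r = 0.2, 1.45 at r = 0.3 and 1.40 at r = 0.5. With an SD of 0.8 the factor goes from 1.37 (r = 0) to 1.31 (r = 0.5); with 1.5 it goes from 1.80 to 1.66.

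**Limit of the check.** This is a one-visit calculation. The planned repeated-measures model, with incomplete data and a single IGA effect across visits, will follow it only approximately.

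**The case against.** The strongest reply is that nothing here is an error. Treatment by visit plus the stratification factor gives a sound randomised comparison, and the gain rests on a correlation that the documents do not supply. That stands.

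There are also reasons to expect a modest correlation. Protocol 9.2.2 has the cream used as needed, stopped on control and limited to courses of three weeks, so Week 16 use follows current more than baseline lesions. Skin where the supplied cream is inadvisable may receive other topicals that are not weighed. SAP 6.6.6 counts unreturned tubes as fully used or unused, which adds noise. Panel 6 separates IGA 3 from IGA 4 partly by whether elevation is extensive, so IGA already carries some area information. All of this lowers the likely gain, but none of it is a reason to leave extent out.

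A reader might infer an inconsistency, because the SCORAD and DLQI models include baseline value by visit. The documents do not support that. Those models adjust for the outcome's own baseline, and TCS amount has none, since the supplied cream starts at Week 0.

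The current model might also be defended by the remark in 14.3.9 about a similar trial. That remark compares transformed with untransformed data and does not address which covariates to include.

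**Conclusion.** The model is valid, and a modest improvement in precision is available at almost no cost. If the partial correlation exceeds about 0.10, adding baseline extent narrows the interval, by about 1.5% to 13% for correlations of 0.2 to 0.5. The cumulative amount probably gains more than the Week 16 amount. These sizes assume the correlation, about 100 subjects and one added covariate.

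Three stronger readings go beyond the documents:
- That the intervals are certainly too wide. Below the break-even the extra term does not help.
- That the estimate is biased, or that chance imbalance in extent passes straight into the ratio. Imbalance acts only through the unknown slope, and the IGA-only interval already allows for it. Data after rescue or IMP discontinuation are excluded under either model, so both rely on data being missing at random; no bias from that source is shown here.
- That the gain is like recruiting a third more subjects. Even r = 0.5 gives an equivalent N of 131.9, and nothing in the documents supports so high a value.

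The endpoints sit in the lowest efficacy tier before the exploratory ones and carry no formal test, so the importance is low.

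**What to change.** Before unblinding, update SAP 6.6.4 so that the main model for both amount and cumulative amount is

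log(Y+1) = treatment × visit + log(baseline BSA) × visit + baseline IGA

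and keep the IGA-only model as a sensitivity analysis. Name a single extent covariate. BSA is the better choice, because EASI mixes severity with area. The target remains the ratio of geometric means, because a baseline covariate in a linear model on the log scale does not change the treatment contrast being estimated.

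Protocol 14.3.16 already provides for reviewing planned analyses against blinded data, so the association of TCS amount with BSA can be examined with the arms pooled before the term is fixed.

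The cost is one slope per visit, eight for Weeks 2 to 16, and about 0.5% in interval width if extent is unrelated to use. No new data are needed. No subjects should be lost, since BSA at baseline is required for eligibility.

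### TCS amount is modelled as log(Y+1) but back-transformed with exp() alone, so the reported means and ratio refer to amount + 1 g

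*Protocol*

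**What the plan says.** Protocol 14.3.9 analyses the amount of TCS used per 2-week period, and the cumulative amount, on a log scale. To allow for zeros ("Due to potential zero valued" amounts), it states that "1 will be added to the values prior to transformation". The model is a repeated measurements model for log(Y+1) with treatment-by-visit and baseline IGA effects, where Y "is either the amount of TCS used or the cumulative amount of TCS used".

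On reporting, the same section says the model estimates are "transformed back to the original scale using the exponential function, thus producing estimated geometric means and estimated ratio of means", each with a 95% CI. The exponential is the only operation named.

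SAP 6.6.4, under the amount of TCS used, adds two assumptions about unreturned tubes but leaves the model alone: "The method used for analysis will be the one specified in the protocol". SAP 6.6.6 defines how the weight used is derived and contains no back-transformation rule.

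Low use is foreseen. Besides the allowance for zeros, Protocol 14.3.9 has a separate binary endpoint: "TCS use (AxMP) <5 g at Week 16 will be analysed according to the primary analysis" used for the primary endpoints.

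**The concern.** The transformation and its stated inverse do not match. Exponentiating a mean of log(Y+1) returns a geometric mean of Y+1, which is not on the original scale of Y. A reader of the trial report would take the arm values as grams of TCS and the ratio as relative TCS use, and neither reading would be right. An arm in which nobody used any TCS would be reported as using 1 g.

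The ratio is affected in one direction only. Adding the same constant to both arms pulls it towards 1, so the relative difference between arms looks smaller, mainly when use is low. Protocol 14.3.5 rules out formal testing, so the estimates and their confidence intervals are the whole result for these endpoints and should be what their label says.

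**Working it through.** The plan states no figure for this point, so there is nothing to reproduce. The check is algebraic, followed by illustrations on assumed amounts.

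**Inputs from the documents.** Offset +1, response log(Y+1), back-transformation exp() (all Protocol 14.3.9); two-sided 95% CIs (14.3.5); about 100 subjects randomised 1:1, so about 50 per arm (14.1). Y is taken in grams, the unit of the <5 g endpoint and of the tube weights.

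**Arm means.** Let m = E[log(Y+1)].
- Planned value: exp(m) = geometric mean of (Y+1).
- Value after undoing the offset: exp(m) - 1.
- The difference is exactly 1 g at any level of use. Relative to exp(m) - 1 that is +100% at 1 g, +20% at 5 g, +10% at 10 g and +1% at 100 g.
- If every subject has Y = 0, then m = 0 and the planned value is exp(0) = 1 g.

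**Ratio.** Let g1 and g0 be the exp(m) - 1 values for tralokinumab+TCS and placebo+TCS.
- Planned: exp(m1 - m0) = (g1 + 1)/(g0 + 1).
- Offset undone: g1/g0.
- For positive g1 and g0, the planned ratio lies between g1/g0 and 1, whatever the distribution of Y.
- The planned ratio also depends on the unit. With g1 = 5 g and g0 = 10 g it is 6/11 = 0.545; with the same amounts in mg it is 5001/10001 = 0.500.

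**Illustration with sampling error.** Assumed: lognormal use, 50 per arm, one visit, no covariate adjustment. E[log(Y+1)] and its SD were obtained by Gauss-Hermite quadrature. For geometric means of 5 and 10 g and log-SD 1:
- exp(m1) = 6.439 and exp(m0) = 11.511; SDs of log(Y+1) are 0.801 and 0.880.
- Planned ratio: 6.439/11.511 = 0.559. SE of the log ratio = sqrt((0.801² + 0.880²)/50) = 0.168. 95% CI: 0.559 × exp(±1.96 × 0.168) = 0.402 to 0.778.
- Offset undone: 5.439/10.511 = 0.517. The delta-method gradients are 6.439/5.439 = 1.184 and 11.511/10.511 = 1.095. SE = sqrt((1.184² × 0.801² + 1.095² × 0.880²)/50) = 0.191. 95% CI: 0.356 to 0.753.

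Other assumed amounts:

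| Geometric means of use (g) | log-SD | Planned ratio | Ratio of exp(m) - 1 |
|---|---|---|---|
| 5 vs 10 | 0.5 | 0.549 | 0.505 |
| 5 vs 10 | 1 | 0.559 | 0.517 |
| 5 vs 10 | 1.5 | 0.573 | 0.535 |
| 20 vs 40 | 1 | 0.518 | 0.507 |
| 50 vs 100 | 1 | 0.508 | 0.503 |
| 400 vs 800 (cumulative) | 1 | 0.501 | 0.500 |

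**Illustration with zeros.** Simulated, 200,000 per arm, log-SD 1, with 20% zeros on tralokinumab and 10% on placebo. Among users, the tralokinumab median is 0.6 times the placebo median. Planned ratio against ratio of exp(m) - 1, by placebo median: 3 g, 0.658 against 0.535; 10 g, 0.556 against 0.500; 50 g, 0.458 against 0.441.

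**The case against.** The strongest reply is that the sentence states its aim, a return to the original scale, and a programmer following that aim could subtract 1 without being told. On that view the wording is incomplete rather than wrong. This has some force for the arm means, but the text attributes its outputs to the exponential step alone. It does not help the ratio: subtracting 1 from an exponentiated contrast is not valid, so the ratio needs either its own derivation or a different label, and the plan has neither.

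A second reply is that exp(m) - 1 is not the geometric mean of Y either. That is true. In the 5 versus 10 g example the assumed geometric means have a ratio of 0.50, the exp(m) - 1 values give 0.52, and the planned output gives 0.56. With any zero amounts the ordinary geometric mean of Y is 0, so every offset summary is a convention. But exp(m) - 1 is the inverse of the transformation used, and it returns 0 when all use is 0.

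A third reply concerns size. Kits of about 180 to 225 g are supplied every second week, and the population has moderate-to-severe disease, so typical use may be well above 10 g. The SAP's two assumptions about an unreturned tube rest on a 100 g content, far more than 1 g. The planned histograms and the <5 g endpoint show use without the log transformation. All of this stands, and it limits the practical consequence.

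**Conclusion.** The concern holds: the back-transformation is wrong as written. Applied literally, it gives geometric means of (amount + 1 g) and a ratio of those means, under a label that promises the original scale. Two results need no assumption about the data: each arm value is exactly 1 g above exp(m) - 1, and the ratio is pulled towards 1. How far it is pulled depends on the level of use, which the documents do not give. On the assumptions above, the effect is visible at around 5 to 10 g per period (0.56 instead of 0.52), small at 20 to 40 g, and negligible from about 100 g or for cumulative use.

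The matter is minor. It touches other endpoints only, no formal test is planned, and the primary and key secondary analyses are unaffected. Whether the CI for the log-scale contrast excludes 0 does not change.

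**What to change.** Add one or two sentences to SAP 6.6.4, for both amount and cumulative amount and under both unreturned-tube assumptions:

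- Arm estimates are exp(LS mean) - 1, with CI limits exp(limit) - 1.
- The exponentiated treatment contrast is labelled as the ratio of geometric means of (amount + 1 g).

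If a ratio without the offset is preferred, report (exp(m1) - 1)/(exp(m0) - 1) with a delta-method or bootstrap CI. It is undefined if the placebo estimate is 0, so the labelled ratio is the simpler choice.

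The cost is the SAP text, one line of code for the arm means and a table footnote. The fitted model and the data collection do not change. Extra programming for a CI is needed only for the ratio without the offset.
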